2.3 Resistance to Platinum-based chemotherapy

Except for testicular cancer, most malignancies have either intrinsic or acquire resistance to platinum-based chemotherapy. Individual aspects of patient and tumor genetic make-ups contribute to these drug resistance phenotypes. Numerous studies have been performed to explore the mechanisms of resistance to platinum [12]. The chemoresistance mechanisms are very complicated and involve more than 700 genes from multiple signaling pathways [13]. Studies exploring individual gene alterations have essentially failed to identify clinically applicable markers for chemoresistance. Chemoresistance mechanisms to platinum agents can be classified into two major groups (**Figure 2**): (1) those responsible for the formation of Pt-DNA adducts (pre-DNA damage mechanisms), and (2) those involved in cellular responses to Pt-DNA adducts (post-damage mechanisms).

2.3.1 Chemoresistance mechanisms related to the formation of Pt-DNA adducts

Modulation of uptake and efflux of platinum compounds by cancer cells

Several studies showed that there is high correlation between decreased Pt accumulation and resistance to Pt [14, 15]. Cellular uptake and efflux of Pt drugs appear to be mediated by transporters and carriers that are shared with copper [16, 17]. However, other studies suggested that passive diffusion plays an important role as well [18-21]. Multiple studies showed that resistance to Pt is associated with active efflux of drugs. For example members of the multi-drug resistance protein (MRP)-related transport proteins are associated with resistance to Pt drugs [22-24]. Cell lines sensitive to cisplatin have lower expression of CTR1, a drug efflux transporter [25]. We found different carboplatin efflux rates between NSCLC cell lines relative to carboplatin IC₅₀ values [26].

Intracellular inactivation of Platinum Agents

Glutathione and other thiols can quench the reactivity of platinum-based drugs with DNA. *In vitro*, there is high correlation between intracellular glutathione levels and resistance to cisplatin [14, 15, 22]. Overexpression of glutathione S-transferase π confers increased resistance to cisplatin in CHO cells [27]. Metallothionein (MT) proteins are a family of sulphydryl-rich proteins that participate in heavy metal binding and detoxification. Overexpression of MT-IIA increases resistance to cisplatin [28], while MT-deficient mice show hypersensitivity to cisplatin [29]. Increased MT was also found in bladder tumors from patients who were unsuccessfully treated with cisplatin chemotherapy [30]. However, the feasibility of these antioxidant proteins as predictive biomarkers of clinical response remains to be demonstrated [31-33].

2.3.2 Chemoresistance mechanisms related to Cellular Responses to Pt-DNA Adducts

Increased DNA Repair

Increased DNA repair capacity has been well documented to correlate with resistance to Pt-based drugs. Testicular cancer is unusually sensitive to Pt, and is deficient in its ability to repair DNA [34]. In several Pt-resistant cancer cell lines, high DNA repair capacity has been observed [15, 32, 35-37].

The mechanisms of DNA repair and its regulation are highly complex. More than a dozen proteins participate in the repair of platinum-DNA damage [38]. For example, the nucleotide excision repair (NER) complex that forms at a site of DNA damage contains at least 15 proteins [39, 40]. The excision repair cross-complementing (ERCC) gene family is an important component of NER complex. Increased ERCC1, ERCC2 and XPA are associated with resistance to Pt [24, 41], and shortened survival in lung cancer patients receiving adjuvant chemotherapy [42]. Similar associations were also observed in breast cancer patients who received carboplatin-based chemotherapy [43]. Although numerous proteins have been evaluated as biomarkers of response to therapy, only ERCC1 has thus far been used as a clinical marker with some success [24].

Increased Tolerance of DNA Damage

There is a significant correlation between increased tolerance of DNA damage and resistance to Pt-based drugs [14, 15]. Several mechanisms contribute to increased tolerance of DNA damage. Some of these mechanisms involve loss of mismatch repair [44], increased DNA replication that bypasses Pt-DNA adducts [45, 46], single nucleotide polymorphisms of cell cycle regulators [43], or decreased apoptosis. Decreased pro-apoptotic, or increased anti-apoptotic gene expression have been shown to participate in resistance to Pt and inhibition of apoptosis [47-49].

2.3.3 Summary of Resistance to Platinum-based Chemotherapy

Owing to the complexity of the above outlined platinum-based drug resistance mechanisms, scoring mutations or gene expression changes in a few individual pathways is likely to have limited impact on developing biomarker tests for predicting

efficacy. The microdosing approach of this feasibility study provides a strategy for obtaining a comprehensive measurement of major resistance factors at play in an individual tumor, since the phenotypic in vivo capacity for Pt-DNA adduct formation and repair can be directly measured in the patient prior to initiation of platinum-based chemotherapy.

2.4 Accelerator Mass Spectrometry (AMS)

AMS was initially developed for geochronology and archaeological research [50, 51]. An AMS instrument is an analytical tool that directly quantifies a very rare isotope (e.g. <1 ^{14}C atom per 109 carbon atoms) in a uniform graphite sample prepared from a biological matrix [52, 53]. The extreme sensitivity of AMS is the result of counting ^{14}C atoms directly instead of counting ^{14}C radioactive decay events (half-life = 5730 years; 6×10^{11} molecules are required for 100 dpm of radioactive decay). Specificity for ^{14}C atoms occurs by instrument design and operation. AMS has been used in the drug research by our co-investigator [name]. of UC Davis, and his colleagues at Lawrence Livermore National Laboratory for the last 15 years. AMS has been used to demonstrate metabolism and pharmacokinetics of several dietary and environmental carcinogens [54-56]. Recently, it has been used to study the metabolism of cancer drugs such as tamoxifen, doxorubicin and carboplatin [57-59]. Compared with the other technologies, the advantage of AMS to detect DNA adducts/damage is its high sensitivity and precision. AMS can detect ^{14}C at the zeptomole (zmole, 10-21 mole; a few hundred thousand molecules per sample) level per mg of carbon with the precision as low as 0.25% [60]. In the application of AMS to cancer research, the chemical dose to be administered to patients for AMS analysis can be minimized to sub-physiological and sub-toxic doses that are not compatible with other less sensitive measurement technologies that require higher doses of chemotherapeutic drugs. Furthermore, the specimen size can be reduced to the amounts that can be obtained from minimally or non-invasive procedures.

2.5 Prediction of Oxaliplatin Exposure

Optimizing the dose of chemotherapy is essential: If the dose is too low it will be ineffective, whereas the toxicity (side-effects) will be intolerable to the patient at excessive doses [61]. The standard method of individualizing chemotherapy dose is based on calculated body surface area (BSA). However, drug absorption and clearance are influenced by multiple other factors, including age, gender, metabolism, disease state, organ function, drug-to-drug interactions, genetics, and obesity [62-66]. As a result, there is high variability in the systemic chemotherapy drug concentration among patients dosed by BSA, and this variability has been demonstrated to be more than 10-fold for many drugs [61, 67]. There is a clear unmet medical need to optimize the dosing of chemotherapy drugs compared to BSA-based calculations.

Of the individual drugs in the FOLFOX regimen, 5-FU has been dose optimized in several clinical studies, and results in significantly better response and survival rates versus BSA dosing [68-70]. For example, in a study involving colorectal cancer patients treated with the FOLFOX regimen, the incidence of serious diarrhea was reduced from 12% in the BSA-dosed group of patients to 1.7% in the dose-adjusted group, and the incidence of severe

mucositis was reduced from 15% to 0.8% [68]. The FOLFOX study also demonstrated an improvement in treatment outcomes. Positive response increased from 46% in the BSA-dosed patients to 70% in the dose-adjusted group. Median progression free survival (PFS) and overall survival (OS) both improved by six months in the dose adjusted group.

The current method (ELISA) for optimizing 5-FU dose is not applicable to oxaliplatin, which is in its free form is a chemically reactive compound that is not amenable to antibody-based quantitation. Other common methods for measuring oxaliplatin (ICP-MS and LC-MS) are complex and lack the throughput needed for clinical testing. In this study, we will use liquid scintillation counting to assess [¹⁴C]oxaliplatin from the plasma ultrafiltrate after administration of a microdose. If successful, we propose to use of a highly sensitive accelerator mass spectrometry (AMS) platform to perform assessment of free drug in plasma ultrafiltrate from clinical samples after administration of a nanocurie dose of [¹⁴C]oxaliplatin, which is amenable to high-throughput analysis. Our goal is to develop a [¹⁴C]oxaliplatin microdosing assay to optimize the use oxaliplatin, such that the delivered AUC is within 10% of the targeted value. The reduction in variation in achieved dose is expected to improve treatment outcome (i.e. response) amongst those who are underdosed, and reduce the development of toxicity (especially neurotoxicity) in those who are overdosed. This proposal is the first step in that project, with the aim of demonstrating the feasibility of using a microdose of [¹⁴C]oxaliplatin to predict the pharmacokinetics of standard BSA-dosed oxaliplatin.

2.6 Assessment of Microdose-induced Oxaliplatin-DNA damage

Several studies have confirmed that the levels of drug-DNA adducts directly correlate with the outcomes of platinum-based chemotherapy, particularly in peripheral blood mononuclear cells (PBMC). After Pt-based chemotherapy, DNA adducts can be detected in multiple tissues [10, 71, 72]. The concentration of Pt-DNA adducts correlates to the drug concentration and incubation time in cell culture [10]. Decreased Pt-DNA adducts are associated with resistance to Pt chemotherapy in cell lines [73]. The levels of DNA adducts, as detected by immunohistochemical staining, correlated with response to Pt chemotherapy [71, 72]. Those patients with low drug-DNA adducts or increased repair of drug-DNA adducts had worse outcomes [74]. Oxaliplatin-DNA adducts have been measured by Pieck et al [75] in peripheral blood lymphocytes from 37 patients with a variety of malignancies. In patients showing tumor response, adduct levels after 24 and 48 h were significantly higher than in nonresponders, indicating that drug-DNA adduct levels in surrogate tissues may serve as biomarkers of response. However, the commonly used drug-DNA adduct detection methods such as atomic absorption spectroscopy, Southern blot, or immunological detection with antibodies, are not sufficiently sensitive for detection of drug-DNA adducts induced by microdose concentrations of platinum drugs. Cell lines and patients need to be exposed to chemotherapeutic doses (high, toxic concentrations) for a sufficient number of drug-DNA adducts to be created for the common adduct detection methods above to be informative [76]. Therefore, these traditional approaches can ONLY identify chemoresistance in patients AFTER full-dose chemotherapy.

In this study, we will adopt the highly sensitive technology of AMS for detection of microdose-induced platinum-DNA adducts. We have shown that AMS is about 1000 times

more sensitive than the traditional approaches for measuring Pt-DNA adducts [58]. Using AMS, we can detect DNA adducts after exposing cell cultures to one microdose of ^{14}C -oxaliplatin. Unique to this AMS-based diagnostic assay is that the biomarker is created de-novo as part of the assay. Consequently, this biomarker assay represents the ultimate pharmacodynamic measurement of all aspects of the alkylating drug in the individual patient's tumor. Given the high concordance of adduct formation in PBMCs with tumor cells, we will perform initial analysis through this surrogate tissue.

As a consequence of administration of a microdose of ^{14}C oxaliplatin, radiolabelled drug molecules interact with DNA to form oxaliplatin-DNA adducts, creating a transient biomarker. With prolonged time, free ^{14}C oxaliplatin is eliminated from serum and cells. Additionally, cells have the capacity to repair oxaliplatin-DNA adducts. In this study, repeated isolation of PBMCs at defined time points will allow for assessment of the kinetics of adduct formation and elimination over time. Using standard techniques for the isolation of genomic DNA and processing steps that minimize the loss of label by DNA degradation, ^{14}C oxaliplatin-DNA adducts can be stably isolated. Using AMS, the oxaliplatin-adduct to DNA mass ratio is calculated as the sample specific $^{14}\text{C}/\text{C}$ ratio minus the background $^{14}\text{C}/\text{C}$ ratio. Using the mass and carbon content of the carrier, the mass of the DNA sample, and the specific activity of the ^{14}C oxaliplatin, an absolute value for the number of ^{14}C atoms per DNA base-pair can be calculated.

2.7 Rationale for the Current Study

While oxaliplatin-based chemotherapy forms the basis of treatment for patients with various gastrointestinal cancers, methods to individualize this treatment based on expected response or observed exposure are urgently needed. For the reasons described in the preceding sections, our ***overall goal*** is to develop a ^{14}C oxaliplatin microdosing assay. The assay will simultaneously 1) individualize oxaliplatin dosing and 2) predict response (or lack thereof) to oxaliplatin-based chemotherapy in individual patients. As an intermediate step toward that goal, the primary aim of this study to test the hypothesis that there is a correlation between the oxaliplatin exposure (AUC in plasma) of patients to a microdose and exposure of patients to a treatment dose. If feasible, such an assay would consistently and accurately predict treatment dose exposure to oxaliplatin. Furthermore, that assessment of DNA adducts formed via the microdose would predict sensitivity and resistance to oxaliplatin-based therapy. Preliminary estimates of these parameters are secondary endpoints of this pilot study.

[figure not shown]
3 DRUG INFORMATION

3.1 Investigational Drug Information

^{14}C Oxaliplatin Solution is an investigational drug synthesized with a ^{14}C label and formulated specifically for this study. The “**microdose**” consists of a combination of the ^{14}C Oxaliplatin Solution and unlabeled Oxaliplatin for Chemotherapy. Prior to administration as a microdose, the correct dose of ^{14}C Oxaliplatin Solution and the correct dose of unlabeled Oxaliplatin for Chemotherapy must be calculated and prepared to achieve the correct patient total oxaliplatin dose and specific radioactivity for this study (see **section 6.3.1** and **section 6.4.1**).

3.1.1 Structural Information

Oxaliplatin

$^{14}\text{C}(\text{*})$ is positioned at all carbons in the cyclohexane ring in ^{14}C -oxaliplatin

Chemical name	$[(1R,2R)\text{-cyclohexane-1,2-diamine}](\text{ethanedioato-O,O'})\text{platinum(II)}$
Chemical abstracts registry number	63121-00-6
Formula	$\text{C}_8\text{H}_{14}\text{N}_2\text{O}_4\text{Pt}$
Molecular weight	397.2858
NCS Number	266046

3.1.2 Mechanism of Action

Oxaliplatin undergoes nonenzymatic conversion in physiologic solutions to active derivatives via displacement of the labile oxalate ligand. Several transient reactive species are formed, including monoquo and diaquo DACH platinum, which covalently bind with macromolecules. Both inter- and intrastrand Pt-DNA crosslinks are formed. Crosslinks are formed between the *N*7 positions of two adjacent guanines (GG), adjacent adenine-guanines (AG), and guanines separated by an intervening nucleotide (GNG). These crosslinks inhibit DNA replication and transcription. Cytotoxicity is cell-cycle nonspecific.

3.1.3 Dosage

The dose of ^{14}C oxaliplatin to be administered as a microdose may need to be modified (see **section 6.3.2**) based on the ^{14}C signal in genomic DNA isolated from patients after receiving one of the dose levels identified in the dose titration table (**Table 1**). The dose levels being evaluated were identified using the following rationale: Based on our ongoing clinical microdosing trial with ^{14}C carboplatin, the radioactive dose of ^{14}C carboplatin is 10^7 dpm/kg of patient body weight with a total carboplatin of 1% of therapeutic carboplatin with AUC of 6. Our pre-clinical studies with oxaliplatin dosing of cell lines indicate that the requirement for ^{14}C oxaliplatin is about 10 times less than ^{14}C carboplatin. We will begin this study at dose level 1, which we have already

demonstrated to be adequate and safe in a single breast cancer patient. Therefore, the start dose (Dose Level 1) of [¹⁴C]oxaliplatin will be 2×10^6 dpm/kg of body weight with the total oxaliplatin at 1% of therapeutic dose (**Table 1**). Based on the ¹⁴C signal in genomic DNA of peripheral blood mononuclear cells (PBMC) in patients after dosing with this dose level 1, the dose will be titrated up or down, if needed, and administered to separate patients with the goal of achieving a ¹⁴C signal at 10-100 times the background. Instructions for preparing the microdose formulation are presented in **section 6.3.1**.

Table 1. Dose titration table

Dose levels	[¹⁴ C]oxaliplatin (dpm/kg of body weight)	Total oxaliplatin (% of therapeutic dose)
-1	1×10^6	1%
1	2×10^6	1%
2	2×10^6	3%
3	10×10^6	3%

3.1.4 Human Toxicity

3.1.4.1 Oxaliplatin Chemical Toxicity.

In this diagnostic feasibility study, patients will receive a small microdose of ¹⁴C-labelled oxaliplatin (1% of therapeutic dose, or less than 3 mg). We do not expect to see any of the clinical side effects associated with standard dose oxaliplatin chemotherapy to occur at this low dose. The most common side effects of standard dose oxaliplatin chemotherapy are presented in **section 3.2.3**.

3.1.4.2 Radiation Toxicity Due to ¹⁴C-label.

Patients will receive minimal radiation exposure (<0.02 mSv) with no expected toxicity.

Drug metabolism with ¹⁴C-labeled drugs using AMS has been studied in healthy volunteers without significant toxicities [77, 78]. We have calculated the radiation dose each patient will receive if he/she participates in this trial. Most oxaliplatin is excreted in urine. The decline of ultrafilterable platinum levels following oxaliplatin administration is triphasic, characterized by two relatively short distribution phases ($t_{1/2\alpha}$ of 0.43 hours and $t_{1/2\beta}$ of 16.8 hours) and a long terminal elimination phase($t_{1/2\gamma}$ of 391 hours). We use 16.8 hours as the half-life for calculation.

For the starting dose, each patient will receive [¹⁴C]oxaliplatin at 2×10^6 dpm/kg of body weight.

$$1 \mu\text{Ci} = 2.22 \times 10^6 \text{ dpm}$$

If the patient's body weight is 75 kg, the total radiation dose *per microdose* will be:

$$2 \times 10^6 \text{ dpm/kg} \times 75 \text{ kg} = 1.5 \times 10^8 \text{ dpm} = 67.6 \mu\text{Ci} \text{ per microdose.}$$

$$1 \mu\text{Ci} = 2.22 \times 10^6 \text{ dpm} \times 0.049 \text{ MeV/disintegration} = 108,780 \text{ MeV/min} = 108,780 \text{ MeV/min} \times (1.6 \times 10^{-13} \text{ joules/Mev}) = 1.74 \times 10^{-8} \text{ joules/min}$$

Therefore, each patient will receive:

$$67.6 \mu\text{Ci} \times (1.74 \times 10^{-8} \text{ joules/min} \cdot \mu\text{Ci}) = 1.2 \times 10^{-6} \text{ joules/min per microdose.}$$

If the average body weight is 75 kg, the radiation dose for each microdose will be:

$$1.2 \times 10^{-6} \text{ joules/min person} \times \text{person} / 75 \text{ kg body weight} = 1.6 \times 10^{-8} \text{ joule/min/kg}$$

We propose that, after 5 half-lives (84 hours), the $[^{14}\text{C}]$ oxaliplatin remaining in the body will be negligible. If the patient is continuously exposed to $[^{14}\text{C}]$ radiation without metabolism of $[^{14}\text{C}]$ oxaliplatin, the radiation dose will be:

$$1.6 \times 10^{-8} \text{ joule/min/kg} \times 60 \text{ min/hr} \times 84 \text{ hr (five half-lives)} = 7.9 \times 10^{-5} \text{ joules/kg}$$

$$1 \text{ joule/kg} = 1 \text{ Sv}$$

The radiation exposure for each microdose will be 7.9×10^{-5} Sv or 0.079 mSv. The radiation exposure for each patient completing both microdoses will be 0.016 mSv.

If this study ends up at Dose Level 3 (10×10^6 dpm/kg, or 5 times the radiation dose used to calculate the above radiation exposure. **Table 1**), and patients undergo both microdose administrations, the radiation exposure will be $0.079 \text{ mSv} \times 5 \times 2 = 0.79 \text{ mSv}$.

The annual effective radiation dose equivalent from natural internal sources is 1.6 mSv per person. The radiation exposure for an abdominal CT scan is 10 mSv. **The radiation exposure to $[^{14}\text{C}]$ oxaliplatin for a patient completing both microdoses on this study is $0.016 \text{ mSv} \div 10 \text{ mSv} = 0.16\%$ of an abdominal CT scan.**

Here, we assume that patients are exposed to $[^{14}\text{C}]$ oxaliplatin radiation at the initial dose for 84 hours without correcting the calculation for reduction of the *in vivo* drug concentration drug by excretion, which makes this a very conservative calculation.

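### Radiation exposure per patient is understated about 10-fold: two microdoses at 0.079 mSv each make 0.158 mSv, not 0.016 mSv

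*Combined protocol and SAP*

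**What the plan says.** Section 3.1.4.2 (Radiation Toxicity Due to 14C-label) makes five statements about exposure.

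- It opens with a general claim: "Patients will receive minimal radiation exposure (<0.02 mSv) with no expected toxicity".
- It works through a dose calculation for a 75 kg patient at the starting level and arrives at 7.9 × 10⁻⁵ "Sv or 0.079 mSv" per microdose.
- It gives the patient total: "The radiation exposure for each patient completing both microdoses will be 0.016 mSv".
- It computes Dose Level 3, which has five times the activity, as 0.079 × 5 × 2 = 0.79 mSv for both microdoses.
- In bold, it states that the exposure "for a patient completing both microdoses on this study is" 0.016 ÷ 10 mSv, or 0.16% of an abdominal CT scan.

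Section 6.1 says that the labelled amount given with cycle 1 of FOLFOX is the same as the amount given in the phase 0 infusion. The two exposures are therefore equal under the section's method.

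**The concern.** A total for two equal doses cannot be smaller than the figure for one. The section gives 0.079 mSv for one microdose and 0.016 mSv for two, and the smaller number is the one used in the bold summary. The opening claim of less than 0.02 mSv is in line with the smaller number and out of line with the derivation.

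The labelled drug is given for research, on top of standard chemotherapy, so this section is where the protocol states the radiation risk that participation adds. A reader who takes only the opening sentence or the bold sentence gets a figure that the calculation between them contradicts.

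**Working it through.** **Inputs, all from Section 3.1.4.2 unless noted**

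- Activity at Dose Level 1: 2 × 10⁶ dpm/kg; body weight 75 kg; 1 µCi = 2.22 × 10⁶ dpm
- Energy per disintegration: 0.049 MeV; 1 MeV = 1.6 × 10⁻¹³ J
- Exposure window: 84 h, five half-lives ("We use 16.8 hours as the half-life for calculation"), with no reduction for excretion
- 1 J/kg taken as 1 Sv
- Abdominal CT scan: 10 mSv; annual natural internal dose: 1.6 mSv
- Two microdoses with the same labelled amount (Section 6.1)
- Activity by dose level (Table 1, Section 3.1.3)

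**Step 1: the single-microdose figure**

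- Activity: 2 × 10⁶ × 75 ÷ 2.22 × 10⁶ = 67.6 µCi
- Energy rate per µCi: 2.22 × 10⁶ × 0.049 × 1.6 × 10⁻¹³ = 1.74 × 10⁻⁸ J/min
- Rate per kg: 67.6 × 1.74 × 10⁻⁸ ÷ 75 = 1.568 × 10⁻⁸ J/min/kg
- Over 84 h: 1.568 × 10⁻⁸ × 60 × 84 = 7.90 × 10⁻⁵ Sv = 0.079 mSv

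This matches the plan. Carrying the printed, rounded rate of 1.6 × 10⁻⁸ instead gives 0.081 mSv, so rounding is not the issue. Activity is set per kg, so body weight cancels and no other weight changes the result.

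**Step 2: both microdoses at Dose Level 1**

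- 2 × 0.079 = 0.158 mSv (0.161 mSv with the rounded rate); stated 0.016 mSv
- Ratio: 0.158 ÷ 0.016 = 9.9
- Share of a CT scan: 0.158 ÷ 10 = 1.58%; stated 0.16%

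The division 0.016 ÷ 10 = 0.16% is itself correct; its input is wrong.

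**Step 3: cross-check within the section**

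The Dose Level 3 total reproduces: 0.079 × 5 × 2 = 0.79 mSv. Dividing by 5 gives 0.158 mSv for both microdoses at Dose Level 1, as in Step 2.

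**Step 4: the opening claim against every dose level, on the same method**

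| Dose level | Activity (dpm/kg) | One microdose (mSv) | Both (mSv) | Both, share of 10 mSv CT |
|---|---|---|---|---|
| −1 | 1 × 10⁶ | 0.040 | 0.079 | 0.79% |
| 1 and 2 | 2 × 10⁶ | 0.079 | 0.158 | 1.58% |
| 3 | 10 × 10⁶ | 0.395 | 0.79 | 7.9% |

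No entry is below 0.02 mSv. One microdose at Dose Level 1 exceeds it by 0.079 ÷ 0.02 ≈ 4. Both at Dose Level 3 exceed it by 0.79 ÷ 0.02 ≈ 40 and amount to 0.79 ÷ 1.6 = 49% of the quoted annual internal dose.

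**Step 5: could excretion explain the stated figures?**

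With exponential loss at the 16.8 h half-life, the 84 h window shrinks to an effective (16.8 ÷ ln 2) × (1 − 1/32) = 23.5 h. One microdose is then 0.079 × 23.5 ÷ 84 = 0.022 mSv and two are 0.044 mSv. Neither is 0.016 mSv or below 0.02 mSv.

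**The case against.** The arithmetic slip is not open to dispute. What can be contested is how far it reaches.

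- *The opening claim states no basis.* It does not say whether it is per microdose or per patient, or worst case or expected, and the section itself calls its calculation very conservative. Section 2.2 reports that about half of oxaliplatin leaves in urine within 6 hours. As an assumption, take half lost exponentially over 6 h, the rest lost with the 16.8 h half-life, and no 391 h terminal phase. The effective exposure is then 6 × 0.5 ÷ ln 2 + 0.5 × 16.8 ÷ ln 2 = 4.3 + 12.1 = 16.4 h. One microdose is 0.079 × 16.4 ÷ 84 ≈ 0.015 mSv, under the claimed limit. This stands for a single microdose, so the factor of 4 holds only on the section's own no-excretion basis. It does not save the patient total: two microdoses are about 0.03 mSv, and the plan never says the claim was derived this way.
- *The 40-fold gap compares an unqualified claim with a conditional dose level.* This is fair. Dose Level 3 is reached only if the signal requires it (Section 6.3.2), and its total is printed openly. The demonstrated decimal error is 10-fold at the starting level; that the opening claim does not cover the titration range is a separate point.
- *The corrected figure is only the section's model carried through.* This also stands. The model stops at 84 h although the section cites a 391 h terminal half-life, so any replacement figure should state its basis.
- *Nothing in the trial's conduct or analysis depends on the figure, and the correct inputs are printed nearby.* This is true, and describing the exposure as minimal is not overturned. It does not excuse a wrong total in a patient risk statement.

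**Conclusion.** The concern holds. On the section's own method (84 hours, no excretion, 1 J/kg taken as 1 Sv), a patient completing both microdoses at Dose Level 1 receives 0.158 mSv. The stated 0.016 mSv is about 10-fold too low. The pattern fits a misplaced decimal point, since 0.158 rounds to 0.16. Damage from PDF conversion is unlikely, because 0.016 appears twice, the 0.16% is computed from it, and the opening claim agrees with it.

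The corrected exposure is still about one-tenth of the quoted annual internal dose (0.158 ÷ 1.6 = 9.9%). The matter is therefore the accuracy of the stated risk, not evidence of harm. It must be corrected because the statement concerns risk to each patient and errs in the favourable direction.

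Two things cannot be settled from the documents. The consent form is not in the reviewed text, so whether it repeats the figure is unknown. The statement in Section 2 that each microdose is below one chest X-ray cannot be checked, because no chest X-ray dose is given.

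**What to change.** In Section 3.1.4.2:

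- Change the total for both microdoses at Dose Level 1 from 0.016 to 0.158 mSv.
- Change the bold comparison to 0.158 ÷ 10 mSv = 1.6% of an abdominal CT scan.
- Replace the opening limit of 0.02 mSv with about 0.16 mSv for both microdoses at Dose Level 1, rising to 0.79 mSv at Dose Level 3.
- Say beside these figures that they assume 84 hours of exposure with no excretion.

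Then check every document that takes its radiation statement from this section, including the consent form, and correct it where the old figures appear.

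The cost is a text amendment. No administered activity, endpoint, sample size or analysis changes. The stated exposure becomes less favourable but remains small beside the section's own comparators.
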